6.2.4. Exploratory Analysis

As an exploratory analysis, [REDACTED]
[REDACTED]
[REDACTED]. The overall results will be presented.

6.2.5. [REDACTED]

[REDACTED]

- [REDACTED]
- [REDACTED]
- [REDACTED]
- [REDACTED]
- [REDACTED]

[REDACTED]

[REDACTED]

6.3. Secondary Efficacy Endpoints and Analyses

The secondary efficacy endpoints are listed in Section 1.2. Analyses will be based on the FAS and PP analysis sets [REDACTED].

As exploratory analyses, endpoints analyzed using an ANCOVA method will be also analyzed using MMRM method in a manner analogous to the analysis as described in Section 6.2.3.2. The analysis windows will be specified in the related section.

6.3.1. Proportion of Patients with a $\geq 50\%$ Reduction from Baseline in the Weekly Average Number of CH Attacks During the 4-Week Period After the First Dose of the IMP

This secondary efficacy endpoint will be analyzed using Cochran-Mantel-Haenszel (CMH) test stratified by baseline preventive medication use (yes or no). Descriptive statistics (count and percent) and p-value for Row Mean Scores difference will be presented.

CH attacks will be derived from the e-diary data as described in Section 6.1.1. The analysis will be based on weeks 1 to 4 analysis window which will be derived using the algorithm described in Section 6.1.3. The weekly average number of CH attacks will be calculated based on data available and prorated to 7 days using formula [1]. Missing data handling methods are provided in Section 6.1.4.2.

The proportion of reduction for a patient will be calculated using formula [2]. Responders will be those with $\geq 50\%$ reduction.

6.3.2. Mean Change from Baseline in the Number of Cluster Headache Attacks

The following 2nd and 3rd secondary efficacy endpoints will be analyzed using an MMRM method in a manner analogous to the analysis as described in Section 6.2.3.2 with month and month-by-treatment interaction in the model instead.

- the mean change from baseline (run-in period) in the number of CH attacks during the 12-week period after administration of the first dose of the IMP, ie, based on week 0 to 12 data
- the mean change from baseline (run-in period) in the number of CH attacks during the 4-week period after administration of the third dose of the IMP, ie, based on week 8 to 12 data

Postbaseline data will include data from three 4-week analysis windows (weeks 1 to 4, weeks 5 to 8, and weeks 9 to 12) derived using the algorithm described in Section 6.1.3. CH attacks within each analysis window will be derived from the e-diary data as described in Section 6.1.1. The weekly average of number of CH attacks for a patient in each analysis window will be calculated and prorated to 7 days using formula [1]. Missing data handling methods are provided in Section 6.1.4.2.

The analysis will be based on data from all three 4-week analysis windows. Results for each endpoint will be subsetted from PROC MIXED outputs. For the 2nd secondary endpoint, the overall results will be presented; for the 3rd secondary endpoint, the results from the weeks 9 to 12 analysis window will be presented.

6.3.3. Mean Change from Baseline in the Weekly Average Number of Days with Use of Cluster-Specific Acute Headache Medications (Triptans and Ergot Compounds) During the 12-Week Period After Administration of the First Dose of the IMP

Use of triptans and ergot compounds for CH will be recorded in the e-diary. The 12-week period is the period from administration of the first dose of the IMP to the EOT/early withdrawal visit. The weekly average number of days with use of triptans or/and ergots for CH for a patient during 12-week period will be calculated and prorated to 7 days using formula [1]. Missing data handling method is provided in Section 6.1.4.2.

Data will be analyzed using an ANCOVA method in a manner analogous to the primary endpoint as described in Section 6.2.2.

MMRM analysis will be based on weekly analysis windows. Data in weekly analysis windows will be derived.

6.3.4. Mean Change from Baseline in the Weekly Average Number of Days Oxygen is Used to Treat Episodic Cluster Headaches During 12-week Period After Administration of the First Dose of the IMP

Use of oxygen will be recorded in the e-diary. The 12-week period is the period from administration of the first dose of the IMP to the EOT/early withdrawal visit. The weekly average number of days using oxygen for a patient during the 12-week period will be calculated and prorated to 7 days using formula [1]. Missing data handling method is provided in Section 6.1.4.2.

Data will be analyzed using an ANCOVA method in a manner analogous to the primary endpoint as described in Section 6.2.2.

MMRM analysis will be based on weekly analysis windows. Data in weekly analysis windows will be derived.

6.3.5. Patient-Perceived Satisfactory Improvement at 1, 4, 8, and 12 Weeks After Administration of the First Dose of the IMP Relative to Baseline

The PPSI scale will be completed in the e-diary at home at week 1 (day 7) and in the investigational site tablet at the visits 2, 3, 4, and 5. Patients will mark the level of CH-associated pain and indicate the level of pain using the following scale compared with 4 weeks ago:

- 1 = Much worse
- 2 = Moderately worse
- 3 = Slightly worse
- 4 = Unchanged
- 5 = Slightly improved
- 6 = Moderately improved
- 7 = Much improved

PPSI will be defined as change in pain that corresponds with a minimal rating of “slightly improved” (Protocol Section 6.7). For analysis purpose, a dichotomous scale of “Responder” (scales 5 to 7) or “Non-responder” (scales 1 to 4) will be derived.

The percentage of patients in dichotomous scale of “Responder” or “Non-responder” at week 1, visit 3, 4, and 5 will be analyzed using a CMH method in a manner analogous to the first secondary endpoint as described in Section 6.3.1. Missing scores will not be imputed.

Modification to SAS code in Section 6.3.1: adding a ‘by’ statement for visit.

Raw scales will be summarized using descriptive statistics. A missing category will be presented if applicable.

6.4. Exploratory Efficacy Endpoints and Analysis

Exploratory efficacy endpoints are listed in Section 1.5. [REDACTED].

[REDACTED]

Section 6.2.3.2. The analysis windows will be specified in the related section.

6.4.1. [REDACTED]

The following exploratory efficacy endpoints will be analyzed [REDACTED]

[REDACTED]

[REDACTED]

[REDACTED]

[REDACTED]

[REDACTED]

6.4.2. Mean Change from Baseline in the Number of CH Attacks During Weeks 1, 2, 3,

[REDACTED]

[REDACTED]

[REDACTED]

[REDACTED]

[REDACTED]

[REDACTED]

6.4.3. [REDACTED]

[REDACTED]

[REDACTED]

6.4.4. [REDACTED]

[REDACTED]

[REDACTED]

- [Redacted]

[Redacted]

[figure not shown]
[Redacted]

[Redacted]

[Redacted]

[Redacted]

[Redacted]

[Redacted]

6.4.7. [Redacted]

[Redacted]

The derivation of input data for this analysis is the same as the primary analysis except only

[REDACTED]

6.4.8.

[REDACTED]

6.4.8.1.

[REDACTED]

[REDACTED]

6.4.8.2.

[REDACTED]

[REDACTED]

6.4.8.4. [REDACTED]

[REDACTED]

[REDACTED]

6.4.8.5. [REDACTED]

[REDACTED]

[REDACTED]

[REDACTED]

[REDACTED]

[REDACTED]

6.4.8.6. [REDACTED]

[REDACTED]

Statistical Analysis Plan

[Redacted]

- | [Redacted]
- | [Redacted]
- | [Redacted]
- | [Redacted]
- | [Redacted]
- | [Redacted]
- | [Redacted]

[Redacted]

[Redacted]

[Redacted]

[Redacted]

[figure not shown]
8. SAFETY ANALYSIS

8.1. General

The safety analysis set will be used for all safety analyses. Summaries will be presented using descriptive statistics by treatment group and all fremanezumab as actually received unless otherwise stated.

8.2. Duration of Exposure to Study Drug

At the visit 2, each patient will receive a 1-hour iv infusion and 3 sc injections of fremanezumab or placebo. At visits 3 and 4, patients will receive 1 sc injection of fremanezumab or placebo.

Duration of the treatment period (days), duration of iv infusion (minutes), dosing visit interval (days), the number of doses received, total number of injections received (placebo or fremanezumab), and reasons for IMP not administrated will be summarized using descriptive statistics. Summary will be presented by treatment group.

IMP administration and accountability data will be listed.

8.3. Adverse Events

Adverse events will be recorded from time informed consent is obtained through the end of study participation.

The following are considered protocol-defined adverse events of special interest to be sent to the sponsor's Global Patient Safety and Pharmacovigilance Department for evaluation: ophthalmic-related adverse events of at least moderate severity, events of possible drug-induced liver injury (aspartate aminotransferase or alanine aminotransferase $\geq 3 \times$ the upper limit of normal [ULN], total bilirubin $\geq 2 \times$ the ULN, or international normalized ratio >1.5), Hy's Law events, or events of anaphylaxis and severe hypersensitivity reactions.

All adverse events will be coded using MedDRA (version 18.1). Each patient will be counted only once in each preferred term or SOC category for the analyses of safety. Summaries will be presented for all adverse events (overall and by severity), adverse events determined by the investigator to be related to test IMP (defined as related or with missing relationship) (overall and by severity), serious adverse events, and adverse events causing withdrawal from the study. Adverse events with the missing flag indicating serious will be excluded from the summary of serious adverse events but included in the summary of non-serious adverse events.

Summaries for injection site and infusion-related adverse events and protocol-defined adverse events of special interest will be presented (overall and by severity).

Listings for deaths, serious adverse events, adverse events leading to discontinuation, injection site and infusion-related adverse events, and protocol-defined adverse events of special interest will be presented. In addition, listings for MedDRA dictionary terms for adverse event descriptions and adverse event preferred terms by patient number and treatment group will be presented.

Spontaneous abortion or an elective abortion due to developmental anomalies will be reported as a serious adverse event (protocol Section 7.2). These serious adverse events will be listed separately if applicable.

Summaries will include treatment-emergent adverse events which are defined as adverse events occurring at or after the first dose of the IMP. The listing will include all adverse events recorded.

Adverse events for patients who did not meet screening criteria will be listed.

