3.2. Planned Number of Patients and Countries

A total of approximately 300 patients (approximately 100 patients per treatment group) are planned to be enrolled in this study. Details on definition of evaluable patients and sample size are given in Section 9.

The study is planned to be conducted in approximately 12 countries in approximately 80 investigational centers. The study is expected to start in Q4/2016 and last until approximately Q2/2018.

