The onset and end dates, duration (in case of adverse event duration of less than 24 hours), action taken regarding IMP, treatment administered, and outcome for each adverse event must be recorded on the source documentation and transcribed to the CRF.

The relationship of each adverse event to IMP and study procedures, and the severity and seriousness of each adverse event, as judged by the investigator, must be recorded as described below.

Further details are given in the Safety Monitoring Plan

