If data are processed from other sources (eg, central laboratory, bioanalytical laboratory, central image center, electronic diary data, ePRO tablet), these data will be sent to the investigational center, where they will be retained but not transcribed to the CRF, unless otherwise noted in the protocol. These data may also be sent electronically to the sponsor (or organization performing data management). All patient data must have supportive original source documentation in the medical records, or equivalent, before they are transcribed to the CRF. Data may not be recorded directly on the CRF and considered as source data unless the sponsor provides written instructions specifying which data are permitted to be recorded directly to the CRF.

For patients who enter a study but do not meet entry criteria, at a minimum, data for screening failure reason, demography, and adverse events from the time of informed consent will be entered in the CRF.

Data Quality Control

Data Management is responsible for the accuracy, quality, completeness, and internal consistency of the data from this study. Oversight will be carried out as described in the sponsor’s SOPs for clinical studies. Day to day data management tasks for this study are delegated to a contract organization, and these functions may be carried out as described in the SOPs for clinical studies at that organization. These SOPs will be reviewed by the sponsor before the start of data management activities.

Data will be verified by the study monitor using the data source, and reviewed by Data Management using both automated logical checks and manual review. Data identified as erroneous, or data that are missing, will be referred to the investigational center for resolution through data queries. Any necessary changes will be made in the clinical database, and data review and validation procedures will be repeated as needed. Data from external sources will be compared with the information available in the CDMS and any discrepancies will be queried.

Applicable terms will be coded according to the coding conventions for this study.

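### SAP 8.3 counts adverse events with a missing seriousness flag as non-serious, the reverse of its rule for missing relationship, so the tabulated SAE count can only be understated

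*SAP*

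**What the plan says.** SAP 8.3 (Adverse Events) sets two defaults for missing classification data in one paragraph.

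- Seriousness missing: "Adverse events with the missing flag indicating serious will be excluded from the summary of serious adverse events". The rest of that sentence moves such events to the other side of the split: "but included in the summary of non-serious adverse events".
- Relationship missing: treatment-related events are "defined as related or with missing relationship", so a blank counts as related.

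Protocol 9.7 (Safety Analysis) has the same relationship rule and says nothing about missing seriousness. The favourable default for seriousness therefore appears only in the SAP.

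Other provisions limit how often the rule would operate. Protocol 7.1.2 makes the field mandatory: "the severity and seriousness of each adverse event, as judged by the investigator, must be recorded as described below". Protocol Appendix S sends gaps back to the site: "Data identified as erroneous, or data that are missing, will be referred to the investigational center for resolution through data queries". On visibility, SAP 8.3 adds: "The listing will include all adverse events recorded".

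**The concern.** A flag that is still blank at database lock is one that mandatory recording and querying failed to settle. Coding it as non-serious asserts something nobody has established, and does so in the direction that makes the safety table look better. For relationship, the SAP takes the cautious course when the information is absent. For seriousness it does the opposite without explanation.

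What is at stake is the tabulated SAE count. SAE numbers may well be low in a 12-week trial of this size, and a single event is easily noticed in a small table.

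There is also a loose end in the drafting. The sentence sends the event to a summary of non-serious events, but the SAP's list of planned adverse event summaries names no such table.

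**Working it through.** No figure in the plan depends on this rule, so there is nothing to reproduce. The check is a comparison of the two rules, followed by a scale calculation.

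**Direction of each rule**

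- Blank relationship: the event enters the related summary. Compared with the true classification, that count can be too high but not too low.
- Blank seriousness: the event leaves the SAE summary. Compared with the true classification, that count can be too low but not too high.

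**Scale.** Let n be the arm size, k the number of patients with an event flagged serious, and m the number of further patients whose only potentially serious event has a blank flag.

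- SAE incidence under the SAP rule: k/n.
- SAE incidence with blanks counted as serious: (k + m)/n.
- The true value lies between these two, so the SAP rule reports the lower bound.
- Difference: m/n.

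Inputs: n = 100, from Protocol 3.2 ("approximately 100 patients per treatment group"). The documents give neither expected SAE counts nor expected numbers of blank flags, so k = 0 to 3 and m = 1 to 3 are assumptions that serve only to show scale.

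| k | m | SAP rule | Blanks counted as serious |
|---|---|---|---|
| 0 | 1 | 0/100 = 0% | 1/100 = 1% |
| 1 | 1 | 1/100 = 1% | 2/100 = 2% |
| 1 | 3 | 1/100 = 1% | 4/100 = 4% |
| 3 | 1 | 3/100 = 3% | 4/100 = 4% |
| 3 | 3 | 3/100 = 3% | 6/100 = 6% |

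Each affected patient is worth 1/100 = 1 percentage point. With m = 0 the two rules give the same table. A patient who also has a flagged SAE is already counted and adds nothing to overall incidence.

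**Between arms.** If the active arm has m₁ such patients and placebo has m₀, the difference in incidence moves by (m₁ − m₀)/100. This is zero when blanks are equally frequent and can take either sign otherwise.

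**The case against.** The strongest reply is that the rule will almost never operate. Seriousness must be recorded for each event, missing data are queried, and SAP 2.5.2 runs the analyses only after final database lock. Every SAE must also reach the sponsor within 24 hours on a separate form (Protocol 7.1.5.3.1), so a real SAE should leave a second record. On this view the asymmetry is reasonable: relatedness is a judgement, so a blank says little, whereas seriousness rests on listed outcomes that trigger a form, and a blank with no form behind it is more likely to be non-serious.

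Most of this stands, and it is why the point is minor. It does not justify the direction of the rule. The SAP sentence does not depend on whether an SAE form exists; it applies to every blank. Appendix S provides for comparing external data with the clinical database, but it does not name the SAE forms as one of those sources. If the absence of a form is the reason for the default, the plan should require that check.

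Three stronger inferences are tempting, and the documents do not support them.

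- *The event disappears from the report.* It stays in the summary of all adverse events and in the listing. Deaths have a listing of their own, and SAP 8.8.1 places cases meeting Hy's law within SAE reporting.
- *The rule matters more because there is no data monitoring committee.* Protocol 5.9.3 confirms there is none, but this table is produced after lock. During the trial, SAEs are reviewed as they are reported (Protocol 3.4), and a tabulation rule does not affect that.
- *One event distorts the arm comparison by 33% to 100%.* Those percentages are 1/3 and 1/1, one event over an assumed 3 or 1. Safety is summarised descriptively (Protocol 9.7, SAP 8.1), and the rule is identical in every arm, so it favours none by design.

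**Conclusion.** The point holds as a minor one. SAP 8.3 resolves missing seriousness in the favourable direction, opposite to its own treatment of missing relationship, and nothing elsewhere in the two documents overrides it. The effect is confined to the tabulated SAE summary. It is about 1 percentage point of SAE incidence per affected patient in an arm of about 100, and nothing if every flag is complete at lock. That size assumes that a flag remains blank, that the event was truly serious, and that the patient has no other SAE. The documents give no basis for expecting more than an occasional case. Expedited reporting and efficacy inference are not affected.

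**What to change.** Replace the sentence in SAP 8.3 with:

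> Missing seriousness flags will be queried and reconciled against the SAE forms before database lock; any event whose seriousness is still missing will be counted as serious in the SAE summary, shown in a separate 'seriousness missing (imputed serious)' row, and marked as imputed in the listing.

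The reconciliation should resolve most blanks on evidence, so the default applies only to what is left. The new sentence also removes the reference to a summary that the SAP does not otherwise list.

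The cost is one SAP sentence and a reconciliation step before lock. The downside is that a non-serious event with an unresolved flag may appear in the SAE table. Because the tables are run after lock, it would stay there in the final report, but the separate row and the listing mark would let a reader discount it. If the sponsor prefers to keep the present rule, the SAP should say why it runs opposite to the one for relationship.

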8.4. Injection Site Assessments

Injection site assessments will be performed immediately (+10 minute) and 1 hour (± 15 minutes) after receiving each dose of the IMP at visits 2, 3 and 4. The injection site(s) will be assessed for erythema, induration, and ecchymosis. More details are in Section 7.11 of the study protocol.

Injection-site reactions should be recorded as adverse events. Injection-site related adverse events will be summary as indicated in Section 8.3.

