7.11. Injection Site Assessments

Injection site assessments will be performed immediately (+10 minutes) and 1 hour (±15 minutes) after receiving each dose of the IMP. The injection site(s) will be assessed for erythema, induration, and ecchymosis.

Severity will be graded according to the following criteria:

- Injection site erythema, induration, and ecchymosis will be graded according to measurements: absent, 5 to ≤50 mm (mild), >50 to ≤100 mm (moderate), and >100 mm (severe). Induration must be assessed by careful superficial palpation avoiding pressuring or squeezing the injection site.
- For spontaneous report of local pain after the injection, it will be measured as summarized in Table 5.

Table 5: Severity of Pain Scale for Injection Site Assessments

Symptom	Severity grade	Assessment
Pain	0	Absent
	1	Mild
	2	Moderate
	3	Severe

If a patient has severe injection site induration, erythema, ecchymosis, has severe injection site induration, erythema, ecchymosis, or pain at 1 hour after completion of IMP administration, the

patient will be reassessed at 3 hours (± 15 minutes) after completion of IMP administration and hourly (± 15 minutes) thereafter until the reaction is of moderate or less severity.

Appropriate treatment may be provided if necessary, in which case it must be recorded as concomitant medication.

Injection-site reactions (injection site erythema, induration, ecchymosis, and pain) should be recorded as adverse events.

8. ASSESSMENT OF PHARMACOKINETICS/BIOMARKERS/ PHARMACOGENOMICS/IMMUNOGENICITY/ANCILLARY STUDIES

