1.3. Safety Endpoints

The safety endpoints are as follows:

- occurrence of adverse events throughout the study
- clinical laboratory (serum chemistry, hematology, coagulation, and urinalysis) test results at each visit
- vital signs (systolic and diastolic blood pressure, oral temperature, and pulse rate) measurements at each visit. Note: Oxygen saturation will be measured in cases of suspected anaphylaxis and severe hypersensitivity. Respiratory rate will also be measured in these cases but not as a standard vital sign.

- 12-lead electrocardiogram (ECG) findings at screening, baseline, and week 12
- use of concomitant medication during the study
- clinically significant changes in physical examinations, including body weight
- injection site reaction (ie, erythema, induration, and ecchymosis) and injection site pain assessments
- occurrence of hypersensitivity/anaphylaxis reactions
- suicidal ideation and behavior as measured by the electronic Columbia Suicide Severity Rating Scale (eC-SSRS)

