CH attack information will be captured daily during the double-blind treatment period using an electronic diary device. Assessments of change in quality of life and health status (using the Hospital Anxiety and Depression Scale [HADS], EuroQol-5 Dimension [EQ-5D] questionnaire, 12-Item Short Form Health Survey [SF-12], Impact on Partner and Family questionnaire, and Work Productivity and Activity Impairment [WPAI] questionnaire); satisfaction with treatment (using the PPSI and Patients' Global Impression of Change [PGIC] scale); safety evaluations (including eC-SSRS); blood collection for pharmacokinetics, immunogenicity, biomarker, and pharmacogenomics (unless not allowed per local regulation) analyses; and urine sampling for biomarker analysis will be performed at prespecified time points.

The end of study is defined as the date the last patient attends the end of treatment (EOT)/early withdrawal visit. The study duration will be 21 months from Q4/2016 to Q2/2018.

The study schematic diagram is presented in Figure 1. Study procedures and assessments with their timing are summarized in Table 2 of the study protocol.

Figure 1: Overall Study Schematic Diagram

ECH=episodic cluster headache; IV=intravenous; PBO=placebo; SC=subcutaneous; V=visit. Note: Patients randomized to the 900-mg iv loading dose group will receive 900 mg of fremanezumab administered via an approximately 1-hour iv infusion followed by placebo as 3 sc injections at visit 2 (week 0) and fremanezumab at 225 mg administered as single sc injections (225 mg/1.5 mL) at visits 3 and 4 (weeks 4 and 8, respectively). Patients randomized to the fremanezumab 675-mg sc quarterly group will receive placebo administered via an approximately 1-hour iv infusion followed by fremanezumab at 675 mg administered as 3 sc injections (225 mg/1.5 mL) at visit 2 (week 0) and placebo administered as single sc injections at visits 3 and 4 (weeks 4 and 8, respectively). Patients in the placebo group will receive placebo administered via an approximately 1-hour iv infusion followed by placebo administered as 3 sc injections at visit 2 (week 0) and placebo administered as single sc injections at visits 3 and 4 (weeks 4 and 8, respectively).

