2.2. Randomization and Blinding

Patients will be randomly assigned with stratification based on gender, country, and baseline concomitant preventive medication use (yes or no) in a 1:1:1 ratio to 1 of 3 treatment groups.

- **fremanezumab 900-mg intravenous (iv) loading dose group:** fremanezumab at 900 mg administered via a 1-hour iv infusion and 3 subcutaneous (sc) placebo injections at visit 2 followed by fremanezumab at 225 mg administered as single sc injections (225 mg/1.5 mL) at visits 3 and 4
- **fremanezumab 675-mg sc quarterly group:** fremanezumab at 675 mg administered as 3 sc injections (225 mg/1.5 mL) and a 1-hour placebo iv infusion at visit 2 followed by placebo administered as single sc injections at visits 3 and 4
- **placebo group:** placebo administered via a 1-hour iv infusion and as 3 sc injections at visit 2 followed by placebo administered as single sc injections at visits 3 and 4

The sponsor, investigators, study staff (except for staff involved in bioanalytical analyses and interim analyses [by a third-party, unblinded statistician]), and patients will be blinded to treatment assignment throughout the study.

Randomization will be performed using electronic interactive response technology (IRT), a third-party vendor. The randomization code will be generated by IRT following specifications from the Biostatistics Department. A Teva statistician will be responsible for reviewing the dummy randomization codes, and the final randomization code will be maintained by the third-party vendor in a secure location.

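### The planned injection-site summary mixes active and dummy subcutaneous injections in every fremanezumab column, and SAP 8.4 specifies no table of the graded assessments by visit or time point

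*SAP*

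**What the plan says.** SAP 1.3 lists "injection site reaction (ie, erythema, induration, and ecchymosis) and injection site pain assessments" among the safety endpoints, as does Protocol 2.1. Protocol 7.11 schedules assessments straight after each dose and again at 1 hour. Erythema, induration and ecchymosis are graded by size, and pain on a 0 to 3 scale.

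SAP 8.4 restates the schedule for visits 2, 3 and 4, naming erythema, induration and ecchymosis but not pain. It then gives one analysis: "Injection-site related adverse events will be summary as indicated in Section 8.3". SAP 8.3 provides for this as follows: "Summaries for injection site and infusion-related adverse events and protocol-defined adverse events of special interest will be presented (overall and by severity)". A listing is also planned. The counting rule there is: "Each patient will be counted only once in each preferred term or SOC category for the analyses of safety". SAP 8.1 sets the columns of all safety tables: "descriptive statistics by treatment group and all fremanezumab as actually received".

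SAP 2.2 gives the injections. The iv arm receives "3 subcutaneous (sc) placebo injections at visit 2 followed by fremanezumab at 225 mg administered as single sc injections" at visits 3 and 4. The sc arm receives three active injections at visit 2 and one placebo injection at each of visits 3 and 4. The placebo arm receives placebo throughout.

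None of the text in SAP 8.1 to 8.5 is blacked out. SAP 8.5 gives the hypersensitivity and anaphylaxis assessments their own descriptive summaries, time since dosing and a listing.

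**The concern.** A study-long incidence by arm describes each regimen as a whole. It does not answer the local tolerability question, which is whether a subcutaneous injection of fremanezumab causes more local reaction than the same injection of vehicle. To answer that, an injection's outcome must be tied to its content, and in this design the content changes between visit 2 and visits 3 and 4 in both active arms. The planned tables drop the visit, so they drop the content too.

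The question matters for this product. Protocol 1.3.1 describes administration-site reactions as the most common treatment-emergent events and names several injection-site terms as identified adverse drug reactions. The stake is a descriptive safety statement; no efficacy analysis or error rate is affected.

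**Working it through.** **Injection content per fully dosed patient (SAP 2.2)**

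| Column | Visit 2 | Visits 3 and 4 | Active share |
|---|---|---|---|
| 900-mg iv arm | 3 dummy | 2 active | 2/5 = 40% |
| 675-mg sc arm | 3 active | 2 dummy | 3/5 = 60% |
| All fremanezumab | 3 active, 3 dummy | 2 active, 2 dummy | 5/10 = 50% |
| Placebo | 3 dummy | 2 dummy | 0/5 |

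Every fremanezumab column is mixed. Each patient has 2 time points × 3 visits = 6 scheduled assessments, which the planned table reduces to one count per term.

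**Size of any dilution.** The plan states no figure to reproduce, and the documents give no reaction rates. The rates below are assumptions: p0 is the risk per dummy injection and p1 the risk per active injection.

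*Extreme A: injections within a patient are independent.* P(at least one reaction) = 1 − (1 − p0)^(dummy injections) × (1 − p1)^(active injections). With p0 = 5% and p1 = 10%:

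- Placebo, any time: 1 − 0.95^5 = 22.6%
- iv arm, any time: 1 − 0.95^3 × 0.90^2 = 30.6%, ratio 1.35
- sc arm, any time: 1 − 0.90^3 × 0.95^2 = 34.2%, ratio 1.51
- All fremanezumab: mean of the two arms = 32.4%, ratio 1.43
- Visit 2, three active against three dummy: 1 − 0.90^3 = 27.1% against 1 − 0.95^3 = 14.3%, ratio 1.90
- Visits 3 and 4, two active against two dummy: 1 − 0.90^2 = 19.0% against 1 − 0.95^2 = 9.8%, ratio 1.95

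*Extreme B: reactions are fully patient-determined.* The same 5% of patients react to every injection, and a further 5% react to every active injection only. Any-time incidence is then 5% on placebo and 10% in each active arm, ratio 2.0. Visit 2 also gives 2.0, so nothing is diluted.

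**Range of assumed rates (ratios to dummy)**

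| p0 / p1 | iv arm, any time (A) | sc arm, any time (A) | Visit 2 (A) | Visits 3 and 4 (A) | All comparisons (B) |
|---|---|---|---|---|---|
| 2% / 5% | 1.57 | 1.84 | 2.43 | 2.46 | 2.5 |
| 5% / 10% | 1.35 | 1.51 | 1.90 | 1.95 | 2.0 |
| 5% / 15% | 1.68 | 1.97 | 2.71 | 2.85 | 3.0 |
| 10% / 20% | 1.30 | 1.43 | 1.80 | 1.89 | 2.0 |
| 15% / 30% | 1.26 | 1.35 | 1.70 | 1.84 | 2.0 |

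On the difference scale under A at 5% / 10%, the loss is smaller. The sc arm shows 34.2 − 22.6 = 11.6 points, against 27.1 − 14.3 = 12.8 at visit 2. At 15% / 30% it is larger: 75.2 − 55.6 = 19.6 against 65.7 − 38.6 = 27.1.

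**The case against.** Three stronger readings are tempting, and the documents support none of them.

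*That the graded assessments are never used.* Protocol 7.11 directs that erythema, induration, ecchymosis and pain be recorded as adverse events, and Protocol 7.1.3 takes their severity from the 7.11 grades. Positive graded findings therefore reach the adverse-event table by severity. What is lost is the visit, the time point and the absent results. Protocol 9.7 also promises counts and percentages for categorical safety data in general. It does not name these assessments, and no SAP section applies it to them. The accurate statement is that the SAP specifies no tabulation.

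*That the trial cannot isolate local tolerability.* Adverse-event onset dates are recorded (Protocol 7.1.2), as are the number and location of injections at each dosing visit (Protocol 5.1), and injection-site events are listed. A by-visit split can be derived. It is not prespecified.

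*That the excess is certainly diluted.* Extreme B shows that dilution can vanish, and the truth probably lies between the two extremes.

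Other objections stand in part. By-arm incidence is the randomised comparison of regimens and should stay. Visit 2 is not perfectly clean for the iv arm, whose dummy injections follow a 900-mg active infusion. By visits 3 and 4 both active arms have already had fremanezumab. The text names only the adverse-event route for recording reactions, and Protocol 7.11 ties pain to spontaneous report although footnote z of Protocol Table 2 lists it among the scheduled assessments. Whether every scheduled grade sits in the database therefore needs checking.

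The size scale, which "will be graded according to measurements: absent, 5 to" 50 mm for mild, names no grade for a reaction above 0 and below 5 mm. That is a minor protocol wording matter and does not bear on this point.

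**Conclusion.** The point holds as a gap in the planned summary. For a named safety endpoint, the only specified analysis combines active and dummy injections in both active arms and in the pooled column. This follows from the schedule and needs no assumption.

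The numerical consequence does rest on assumptions. At 5% and 10% per injection, the any-time ratio lies between 1.35 and 2.0 in the iv arm and between 1.51 and 2.0 in the sc arm, depending on how strongly reactions cluster within patients. Visit 2 gives 1.9 to 2.0 in either case, so the by-visit contrast is much less sensitive to that unknown. This is a worthwhile, inexpensive improvement to a descriptive analysis.

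**What to change.** Keep the adverse-event tables and listing. Add to SAP 8.4 one descriptive table of the worst grade per sign (erythema, induration, ecchymosis and pain), including absent, by arm and dosing visit, with each cell labelled by what was injected subcutaneously at that visit. Lay it out so that:

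- the sc arm against the placebo arm at visit 2 is the cleanest contrast, three active against three dummy injections;
- the iv arm at visit 2 is shown separately, because its dummy injections follow an active infusion;
- visits 3 and 4 show the iv arm's active injections, with a note that both active arms have prior exposure;
- arms are compared within a visit, since visit 2 has three injections and the later visits one each.

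If some scheduled grades were captured only as adverse events, state in SAP 8.4 that the visit will be assigned from onset date and the injection record.

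The cost is one more descriptive table and a check of what the database holds. No procedure, dose or patient burden changes.
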